### 5.9 Study Exit or Premature Withdrawal

Subjects will be exited from the study by completion of a Study Exit eCRF. Subjects will be exited upon completion of the follow-up visits, withdrawal of consent, or instance of meeting a primary study endpoint (major amputation or death). Following study exit, the subject will undergo the standard medical care for their condition as determined necessary and appropriate by their physician.

Subjects may be prematurely exited or withdrawn from the study for, including but not limited to, the following reasons:

- Voluntary withdrawal – meaning that the subject voluntarily chooses not to further participate in the study
- Lost to follow-up – meaning that the subject is more than 14 days out of window of a study visit and 3 documented attempts to contact the subject are unsuccessful. A subject who misses two consecutive study visits, including phone contact, will be considered lost to follow-up. A missed visit will be considered a protocol deviation and the deviation will be documented and reported.
- In the physician’s opinion, it is not in the best interest of the subject to continue study participation.

All subjects enrolled (including those withdrawn or lost to follow-up) shall be accounted for and documented.

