**11.3 Determination of Sample Size**

Although the analysis methods are Bayesian, the following frequentist scenarios are used to guide the determination of minimum and maximum sample size.

- According to PASS 13, when using  $\alpha = 0.025$  (one-sided) in an exact binomial test, achieving 90% power to test the hypotheses in Section 7.1 when the true AFS = 0.70 would require a sample size of 101 subjects. Allowing for 10% missing data would require a sample size of N=113 subjects
- If the true AFS = 0.68, a sample size of 101 subjects would achieve 81% power. Allowing for 10% missing data would require a sample size of N=113 subjects
- If the true AFS = 0.75, 90% power requires a sample size of N=56 subjects. Allowing for 10% missing data would require a sample size of N=63 subjects.

There is considerable uncertainty in the true AFS rate  $\phi$ . Consequently, it is desirable to utilize a study design that achieves at least 80% power when  $AFS \geq 0.68$  and 90% power when  $AFS \geq 0.70$ , while allowing early stopping of enrollment if the AFS rate proves to be very high (e.g., 0.75) or very low ( $\leq 0.54$ ). Therefore, the study design was selected wherein the sample size is adaptively determined, with a minimum value of 60 and a maximum value of 120.

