6 PRIMARY ENDPOINT ANALYSIS

The primary endpoint is the Amputation-Free Survival Rate (AFS) at 6 months (180 days). The primary endpoint will be evaluated against a performance goal of 0.54. See Appendix 1 (Section 10) for justification of this performance goal.

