6.2 Statistical Analysis

The statistical methods are Bayesian, and ϕ is assigned a non-informative Beta(1,1) prior distribution. Given a set X of binary observations (amputation-free at 180 days, not amputation-free at 180 days, with no missing data), the posterior distribution $f(\phi | X)$ also follows a Beta distribution, by conjugacy.

The alternative hypothesis will be accepted (and the null hypothesis rejected) if the posterior probability of the alternative hypothesis exceeds a threshold $\psi = 0.977$, where ψ is chosen to control the type I error rate of the design at a level ≤ 0.025 .

Because some missing data are expected, Bayesian multiple imputation will be employed in the principal analysis. More detail on this imputation is given in Sections 6.4, 6.5, and 11.

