6.5 Predictive Model

This section describes the prediction model that is used to predict the 6-month outcomes for subjects who have not yet reached 6 months. This model enables computation of predictive probabilities that form the basis for the sample size decisions in the Goldilocks design; it also serves as the "imputer's model" in the Bayesian multiple imputation that is used in the final inference.

Outcomes at 6 months are binary and are denoted "E" (for having experienced a primary outcome Event) or "N" (for not having experienced an event). At any analysis, it is expected that some subjects will not have completed 6 months, and the 6-month outcomes for those subjects will be imputed based on a statistical model, as described below.

At the time of analysis, subjects will fall into one of three categories:

- A. Status E or N has been observed at 180 days. For example, subject is known to be event-free at 180 days (N), or subject has had a primary event prior to 180 days and at least 180 days has elapsed since that subject entered the analysis cohort (E). (Note: an event at exactly 180 days will count as an event.)
- B. Subject is known to have had an event at time < 180 days, but the subject has not yet had the opportunity to be followed for 180 days. For example, subject dies at Day 100 but the data cutoff date for analysis is only 25 days later, before the subject has the opportunity to be followed for 180 days.
- C. Subject is censored without known event at time < 180 days.

Subjects in Group A have observed 180-day event status and need no imputation. Subjects in Group B will have their 180-day status set to E (with probability 1). Subjects in Group C will have their 180-day outcome imputed to be E with a probability that is subject-specific and is based on how long that subject has been followed and also on the event-free survival experience of other subjects, calculated via a Bayesian piecewise exponential survival model, as follows.

STATISTICAL ANALYSIS PLAN

In this imputation model, the hazard function $h(\tau)$ is piecewise constant over the intervals $[0, 30 \text{ days}]$, $(30 \text{ days}, 60 \text{ days}]$, $(60 \text{ days}, 90 \text{ days}]$, and $(90 \text{ days}, 180 \text{ days}]$. Specifically, let each subject's time to event be modeled such that the survivor function is

$$S(t) = e^{-\int_0^t h(\tau) d\tau}, \text{ where}$$

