The censoring mechanism applied to these simulated event times is induced by the accrual rates, the timing of analyses, and by a random dropout pattern. For every simulated subject, a study start time is assigned according to an assumed accrual pattern, and when an analysis occurs, such as the first sample size evaluation when 60 subjects have been enrolled, each simulated subject's event time is censored at that time (if an event has not previously occurred for that subject). In addition, a designated fraction of simulated subjects is randomly chosen to be lost to follow-up at random times that are uniformly distributed over their 180-day study period, and these subjects are censored at the minimum of the dropout time and the analysis time (assuming they have not yet had an event). For other analysis times (interim or final), censoring times are simply re-computed based on the new time of analysis, and some simulated subjects who did not have an event at the first sample size analysis may have events at a subsequent analysis.

Lost to Follow-up / Data Missingness

Simulations were conducted under the assumption of 10% lost to follow-up (LTFU) over the 6-month study period. With each simulated trial, each subject was designated to be "lost" with probability 0.10; thus, the exact number of subjects designated to be lost from one simulated trial to the next varied, though on average it was 10%. Furthermore, those subjects designated as "lost" were assumed to have been lost uniformly in time over the 6-month period. Subsequent to this, subjects were assigned event times. If the event time occurred after the LTFU time, that subject was considered censored at the LTFU time, whereas if the event time occurred before the LTFU time, that subject had an observed event at the event time.

Rate of Accrual

The speed at which subjects are recruited into the trial is an important assumption embedded within the simulations to determine operating characteristics. The expected rate of accrual into the analysis population is 5 subjects/month, after an initial ramp-up period for the first 7 months of 1, 2, 2, 3, 3, 4, and 4 subjects/month. This "expected" accrual rate was used in the generation of operating characteristics shown in Table 2.

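### Protocol 5.9 lets subjects leave before Day 180 with no required check of limb and vital status, so the primary analysis relies on exit being unrelated to prognosis

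*Protocol*

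**What the plan says.** Protocol 5.9 gives three routes to premature exit: voluntary withdrawal, loss to follow-up, and a physician's judgement, worded as "In the physician’s opinion, it is not in the best interest of the subject to continue study participation". None is tied to Day 180.

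Loss to follow-up is defined twice in the same bullet. The first definition is that "the subject is more than 14 days out of window of a study visit and 3 documented attempts to contact the subject are unsuccessful". The next sentence says "A subject who misses two consecutive study visits, including phone contact, will be considered lost to follow-up". A missed visit on its own is only a protocol deviation. Section 5.9 asks that every enrolled subject be documented, but attaches no outcome check after exit. The telephone assessment in Protocol 5.8 and in the footnotes to Table 1 is for subjects who are out of area or decline a visit.

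In SAP 6.5 (and Protocol 11.5.2), an event-free subject who leaves early belongs to Group C: "Subject is censored without known event at time < 180 days". The Day 180 outcome is drawn from a piecewise exponential model that uses time followed and the pooled hazard. Exit reason, graft status and wound status do not enter.

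SAP 6.7 simulates 10% loss, with subjects chosen at random, and "those subjects designated as 'lost' were assumed to have been lost uniformly in time over the 6-month period". Its sensitivity tables vary only the accrual rate.

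SAP 6 states: "The primary endpoint will be evaluated against a performance goal of 0.54". In SAP 6.2 the posterior threshold of 0.977 is "chosen to control the type I error rate of the design at a level" of 0.025 or less.

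**The concern.** The primary endpoint consists of death and above-ankle amputation. Both can be established without a study visit, yet the exit rules allow them to go unrecorded. The trial has one arm and a fixed goal, so no control group carries an offsetting error. If the subjects who leave are at higher risk than those who stay, each is credited with too high a chance of being event-free, and a device that only equals the goal passes too often. The simulations behind the type I error claim do not test this.

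The two loss definitions add a second problem: two sites could close the same subject at different times, one well before Day 180 and one after it.

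**Working it through.** **1. The plan's own figures.** The exact binomial sizing in Protocol 11.3 and SAP 6.3 reproduces.
- At N=101 and one-sided 0.025, success needs at least 65 event-free subjects. Alpha is 0.0227; power is 0.909 at AFS 0.70 and 0.814 at 0.68.
- At AFS 0.75 the smallest N is 56.
- For 10% missing, 101/0.9 = 112.2, so 113; 56/0.9 = 62.2, so 63.

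The SAP 6.7 hazards also reproduce. The cumulative hazard to Day 180 is 30(0.005417298) + 30(0.00647187) + 30(0.004045362) + 90(0.0015350038) = 0.6162, and exp(-0.6162) = 0.54. The intermediate values are S(30) = 0.85, S(60) = 0.70 and S(90) = 0.62.

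**2. The two loss rules for a missed 3-month visit.** Protocol 5.8 sets a month at 30 days and this visit window at ±2 weeks.
- First rule: window closes at Day 90 + 14 = 104. More than 14 days beyond that is after Day 118, provided three documented contacts have failed.
- Second rule: the next visit is at 6 months, so loss is not declared until Day 180 + 14 = 194.

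The first rule can close the subject 180 - 118 = 62 days before the endpoint date; the second only after it.

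**3. What imputation credits to one exited subject.** The imputed event-free probability after time Q is S(180)/S(Q). If the true hazard after exit is m times the pooled hazard, the correct value is that ratio to the power m. With the SAP's null hazards:

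| Last known event-free | Imputed | True if m=2 | True if m=3 |
|---|---|---|---|
| Day 60 | 0.54/0.70 = 0.771 | 0.595 | 0.459 |
| Day 90 | 0.54/0.62 = 0.871 | 0.759 | 0.661 |

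**4. Effect on the test.** The final analysis was simulated at fixed N=105 with these inputs:
- SAP hazards, Gamma(0.001, 0.001) priors, Bernoulli imputation, Beta(1,1), success if the mean posterior probability exceeds 0.977;
- a fraction d designated to exit at uniform times;
- hazards scaled by k so that true AFS stays at 0.54, solving (1-d)·S(180) + d·E[S(U)·exp(-m{H(180)-H(U)})] = 0.54, where U is the exit time.

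With d = 10%, about 6.8% of subjects are actually censored (0.068 × 105 ≈ 7), because some have their event before leaving. Type I error is shown as the range over repeat runs of at least 4,000 trials where more than one was made:

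| Assumed hazard after exit | Mean estimated AFS | Type I error |
|---|---|---|
| 1x | 0.540 | 0.021-0.028 |
| 2x | 0.550 | 0.031-0.037 |
| 3x | 0.556 | 0.042-0.055 |
| 5x | 0.566 | 0.066-0.072 |
| every exited subject fails | 0.600 | 0.204 |

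At 5% exits and 3x, type I error is 0.031-0.035.

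**5. Comparator.** With Day 180 status known for all 105 subjects, success needs at least 67 event-free, and the exact type I error at 0.54 is 0.0268. This is a fixed-N figure. The SAP's 0.0239 (Table 2) includes the interim stopping rules, which were not simulated here.

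**6. Cross-check.** In the all-fail row, estimated minus true AFS is 0.5999 - 0.5394 = 0.0605. Divided by the censored fraction, 0.0731, this is 0.83. The imputation therefore gives the average exited subject an 83% chance of being event-free, in line with step 3.

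**The case against.** Several points on the other side are sound.

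- **Single missed visit.** A reader might infer that one missed visit is enough for exit. It is not: the first loss rule also needs three failed documented contacts. Exit is also permissive, and nothing forbids a later attempt at contact. But nothing requires one.
- **Upward bias as a fact.** A reader might conclude that AFS is biased upward. The documents contain no data on the prognosis of exited subjects. A failing graft as the usual reason for physician exit is conjecture; the protocol manages graft failure within the study, through secondary patency and adjudicated re-interventions. At equal hazard the simulated bias is nil.
- **Tipping-point analysis.** Protocol 11.5.3 and SAP 9.1.1 plan to take every missing Day 180 outcome as event or non-event in all combinations, and to examine the reasons for missingness. This does not assume random exit and would expose a fragile result. It is a sensitivity analysis, however: it leaves the primary decision unchanged and cannot recover uncollected outcomes. The completers-only and six-piece analyses share the primary analysis's assumption.
- **Adverse event duties.** Protocol 8.1 has related and index-limb serious events followed until they resolve, stabilise or are explained, or the subject is lost. Section 8.5 has all serious events reported through 6 months and index-limb ones through 3 years. Neither says whether the duty survives exit, and neither secures Day 180 status in a subject with no reported event.
- **Size.** The multiples are assumed and applied to all exits, at a 10% rate that SAP 9.1.1 treats as an upper expectation. The documents do not split exits by reason, so the share due to the physician clause is unknown.

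**Conclusion.** The gap is in the text: exit before Day 180 is allowed, two loss definitions conflict, and no available provision requires limb and vital status at Day 180 afterwards. The primary result then rests on exit being unrelated to prognosis, an assumption the SAP's simulations never relax.

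The consequence is conditional. At two to three times the hazard after exit, AFS is overstated by about 1 to 1.7 points and type I error is roughly 0.03 to 0.055, against 0.027 with complete data. The all-fail figure of 0.204 is an extreme bound, not an expectation. These sizes rest on assumed multiples, 10% designated exits, fixed N=105 and the final analysis only. Some protocol pages, including consent material, were not available. The point deserves a change because the missing outcomes are largely avoidable; the documents do not show that bias has occurred or will.

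**What to change.** In Protocol 5.9, separate stopping study visits from ending AFS ascertainment:

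1. Reconcile the two loss sentences into one definition.
2. For the primary endpoint, do not close a subject as lost or by physician decision until an attempt has been made, on or after Day 180, to obtain AFS status.
3. For every subject who stops visits early, except one who withdraws consent to further data collection, record index-limb and vital status at Day 180 from telephone contact, the treating physician, medical records or public death records. Enter it as an observed outcome (Group A in SAP 6.5).

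The cost is protocol wording, possibly a consent line allowing record checks, and a call or record search for roughly 7-10 subjects. After three failed contacts a call alone may not suffice. Some subjects will stay unrecoverable: if half did (an assumption), type I error would still be about 0.035 at 3x and 0.042 at 5x. The change reduces the possible bias but does not remove it.

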## 6. System Accountability

Access to LimFlow System inventory will be controlled and will be housed in a secure location. Records will be maintained to document the physical location of inventory from shipment/removal from Sponsor facility through use and/or return or disposal.

The site will be responsible for keeping the Device Accountability Logs up to date, which record receipt, use, return and/or disposal of each investigational device.

If there is a product malfunction or other need to return the system or system components to the Sponsor, the Sponsor should be contacted for safe product disposal and/or return. Specific instructions will be provided in the Manual of Operations.

## 7. Safety Oversight

### 7.1 Independent Review Committee (IRC)

The Independent Review Committee specific criteria to be evaluated in the determination of patient eligibility include, but may not be limited to:

- Baseline angiograms/images to evaluate the status and patency of the distal arterial bed (i.e., anterior /posterior projections of below the knee and foot views of tibial and peroneal arteries, dorsalis pedis artery, and plantar arteries).
- Wound photographs of all wounds
- Additional exams if required to confirm eligibility

### 7.2 Clinical Events Committee (CEC)

The Clinical Events Committee (CEC) will be responsible for the review of all device- or procedure-related adverse events and adjudication of study endpoint events according to the CEC charter. The details of the CEC objectives, scope of responsibilities, meeting schedule, record keeping, and other committee

administration details will be outlined in the CEC Charter and further agreed to by the committee members. CEC adjudicated events will be used in the analysis of study endpoint data.

The CEC will adjudicate the events related to the endpoints as listed below and all UADEs. The CEC will also review other events when requested to do so by Sponsor.

Events reviewed by the CEC:

**Outcomes Adjudication:** Reports of endpoint event components will be reviewed and adjudicated, including but not limited to:

- Target Limb amputation documented at ankle or above
- Target Limb Occlusion (via DUS and/or angiographic documentation)
- Target Limb Thrombosis (via DUS and/or angiographic documentation)
- Death
- Major and minor re-interventions of the index limb
- Contrast-induced nephropathy within 72 hours of the index procedure

The CEC will also review safety data while the study is in progress, including reports of any serious device- or procedure-related adverse events and/or any reports of device malfunction or failure.

### 7.3 Data Monitoring Committee (DMC)

The Data Monitoring Committee (DMC) will make a recommendation to the sponsor regarding sample size re-estimation. This will be based upon the information provided to them by the independent statistician that will implement the adaptive sample size re-estimation. During the study, the DMC will be asked to ensure that the rights and welfare of the subjects are protected by providing recommendations concerning the continuation, modification, or termination of the study based on review of safety data. Additional DMC details will be outlined in the DMC Charter and further agreed to by committee members.

### 7.4 Study Termination

If the Sponsor determines that an event, or event rate presents an unreasonable risk to subjects, then the investigation or parts of the investigation presenting that risk shall be immediately revised or terminated. Termination shall occur not later than 5 working days after the Sponsor makes this determination and not later than 15 working days after the Sponsor first received notice of the event. The Sponsor will notify all participating investigators, and IRB/ECs and the FDA of the termination of the investigation.

## 8. Adverse Event and Incident Reporting

Adverse events (AEs) may occur during the investigational procedure or during the follow-up phase. Existing medical conditions prior to patient enrollment will be documented in the subject's medical record but should not be reported as adverse events that are related to the investigational device or procedure unless significant exacerbation of the pre-existing medical condition resulted directly from the device or the procedure. Adverse Events determined to be relevant to the indication being studied will be recorded and reported to the Sponsor.

At each evaluation, the investigator (or designee) will determine whether any adverse events (AEs) relevant to the indication being studied have occurred. Subjects are encouraged to report AEs spontaneously or in response to general, non-directed questioning (e.g., How has your health been since the last visit?). If it is determined that a relevant AE has occurred, the investigator should obtain all the information required to complete the AE Case Report Form (CRF).

Each adverse event will be judged by the Investigator as to its relationship and level of relatedness to the investigational devices and/or investigational procedure. In addition, the Investigator will identify the date of onset, any required treatment or intervention, severity and duration. All adverse events will be monitored until they are adequately resolved or explained. The CEC will be the final arbiters of AE seriousness, severity, classifications, relatedness, and anticipatedness.

For purposes of this study, the following events are not considered adverse events, because they are normally expected to occur in conjunction with endovascular procedures / post-procedure, or are associated with customary, standard care of subjects undergoing these procedures:

- Early post-operative pain (within 24 - 48 hours post-index procedure) at the access site and/or related to position on procedure table
- Post-anesthesia/conscious sedation emesis, nausea, or headache (within 24 - 48 hours post-index procedure)
- Chest pain without associated ECG changes
- Hematocrit decrease from baseline not associated with hemodynamic changes, remaining above 30% and not requiring transfusion
- Electrolyte/fluid imbalance without clinical sequelae following endovascular procedure, even if requiring correction
- Low grade temperature increase (<38.3°C/101°F)
- Sinus bradycardia/tachycardia that does not require treatment or intervention
- Systolic or diastolic blood pressure changes that do not require treatment or intervention
- Standard wound care for this patient population (e.g., debridement, minor amputations, etc.) including those instances wherein the patient stays overnight for observation

This listing of events is intended to provide guidance to the investigational sites for purposes of adverse event reporting. The investigator at the investigational site should utilize his/her own clinical judgment in evaluating adverse experiences and may decide that the above events should be reported as adverse events.

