**8.4 General AE Definitions**

An AE is defined as any undesirable clinical occurrence in a subject whether or not it is considered to be device related. In addition, the definition of AE applies to any event with an onset post study procedure or to any underlying diseases, present at baseline that exacerbate in severity post study procedure. Therefore, an underlying disease that was present at the time of enrollment is not reported as an AE, but any increase in the severity of the underlying disease is to be reported as an AE.

The following definitions for rating severity of adverse events will be used:

**Mild:** Awareness of signs or symptoms, but easily tolerated; are of minor irritant type; causing no loss of time from normal activities; symptoms would not require medication or a medical evaluation; signs or symptoms are transient. Consider whether these events are clinically significant and relevant to report.

**Moderate:** Interferes with the subject’s usual activity and/or requires symptomatic treatment.

**Severe:** Symptom(s) causing severe discomfort and significant impact of the subject’s usual activity and requires treatment.

**Serious adverse event (SAE)** is defined as an event:

- Results in death
- Is life-threatening
- Requires in-patient hospitalization or prolonged hospitalization
- Necessitates an intervention to prevent a permanent impairment of a body function or permanent damage to a body structure (i.e. revascularization of LimFlow System)
- Results in persistent or significant disability/incapacity
- Results in congenital abnormality

**Adverse Device Effect (ADE) / Device-Related Adverse Event:** an adverse effect on health or safety caused by or associated with the study device. An adverse event is considered to be device-related when, in the judgment of the investigator, the clinical event has a reasonable time sequence associated with use of the investigational device and is unlikely to be attributed to concurrent disease or other procedures or medications. It is reasonable to believe that the device directly caused or contributed to the adverse event.

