#### AMPUTATION

**Major amputation:** amputation of the index limb at the level above the ankle.

**Minor amputation:** amputation(s) of the index limb/metatarsals at the level below the ankle.

**Pre-planned amputation:** minor amputation(s) that are prospectively anticipated as part of the overall procedure and care plan for a subject. These anticipated procedures should be documented in the medical record prior to the index procedure.

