8 SAFETY ANALYSES

Adverse events (AE) will be processed by MedDRA coding with System Organ Class (SOC) and Preferred Term (PT) by a medical monitor. They will be evaluated further for severe adverse event (SAE) categorization. Adverse events will be summarized by tabulating the number and percentages of enrolled subjects experiencing each event through milestone time points. Device- and procedure-related adverse events will be summarized separately.

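### Protocol Section 8 classes minor amputations as non-adverse events with no time limit and no planned/unplanned limit, and no SAP table counts them

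*Protocol*

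**What the plan says.** Protocol Section 8 introduces a list by saying that "the following events are not considered adverse events, because they are normally expected to occur in conjunction with endovascular procedures / post-procedure", or because they belong to customary care. The last item is "Standard wound care for this patient population (e.g., debridement, minor amputations, etc.) including those instances wherein the patient stays overnight for observation". The paragraph after the list softens it: "This listing of events is intended to provide guidance to the investigational sites for purposes of adverse event reporting", and investigators are to use clinical judgment and may report a listed event.

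Other parts of the plan bear on the same event:

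- Section 8.4 says of disease present at enrollment that "any increase in the severity of the underlying disease is to be reported as an AE". In-patient or prolonged hospitalization is one of its SAE criteria.
- Section 8.4 also says that the presenting condition is reported as the AE and a procedure as its treatment. Amputation is one of its examples of treatment.
- Section 15 (Amputation) defines pre-planned amputation as "minor amputation(s) that are prospectively anticipated as part of the overall procedure and care plan for a subject", to be documented before the index procedure. Inclusion criterion 6 allows a planned minor amputation within 30 days.
- Section 7.2 names for adjudication "Target Limb amputation documented at ankle or above". No lower level is named.
- SAP Section 8: "Adverse events will be summarized by tabulating the number and percentages of enrolled subjects experiencing each event through milestone time points".

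**The concern.** The item covers an operation that removes part of the treated foot. It does not separate an amputation that was part of the care plan from one forced by later deterioration, although the protocol has a defined term for the first kind. A site that follows the item as written can conclude that an unplanned minor amputation needs no AE form at all. Another site, following Section 8.4, would report the gangrene, infection or occlusion that led to it.

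The trial is single-arm, so no concurrent control group would show that reporting is uneven. Lower extremity ischemia is among the anticipated adverse events in Section 10.3. Unplanned loss of index-limb tissue is therefore something a reader of the safety tables would expect to find there, counted the same way at every site.

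**Working it through.** No arithmetic applies: the plan states no figure on this point and gives no minor-amputation rate. The check is a comparison of the texts.

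1. **Limits on the other listed items.** Each of them is bounded. The pain item opens "Early post-operative pain (within 24 - 48 hours post-index procedure", and the emesis, nausea and headache item has the same window. Chest pain must be without ECG changes, hematocrit must stay above 30%, electrolyte imbalance must have no clinical sequelae, and temperature must be below 38.3°C. Heart-rate and blood-pressure changes must need no treatment. The wound-care item has only the undefined word standard, and its last clause widens it to overnight stays.

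2. **One event under two rules.** Take a minor amputation of the index limb at Month 4 for advancing gangrene, not planned before the index procedure.
   - Under the Section 8 item, it can be read as standard wound care. No AE is reported, so nothing reaches the tables of SAP Section 8.
   - Under Section 8.4, the gangrene is worsening disease and is the AE, with amputation as treatment. It is an SAE if a seriousness criterion is met, and it is tabulated under the term for gangrene.
   - The convention in Section 8.4 takes effect once a site is reporting an AE. The Section 8 item can stop the site before that step.

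3. **Overnight stays.** Section 8 keeps wound care with an overnight observation stay off the AE list. Section 8.4 makes in-patient hospitalization an SAE criterion. The protocol does not say whether an overnight observation stay meets that criterion.

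4. **Whether the event is picked up elsewhere.**
   - *Collection: yes.* Table 1 has an amputation assessment at every follow-up visit except Month 2, and its footnote 9 calls for review of procedures on the index limb.
   - *Adjudication: not clearly.* The list in Section 7.2 is open-ended but names only amputation at the ankle or above. It also names minor re-interventions, but Section 15 defines these as procedures on the stent graft. Under Section 4.10.5 the medical monitor screens adverse events for adjudication, so an event not reported as an AE may not enter by that route.
   - *Analysis: no count.* Limb Salvage (SAP Section 3.2) concerns above-ankle amputation only. SAP Section 8 tabulates coded AEs, so an amputation recorded as treatment is not counted even at a site that reports the condition. SAP Section 9.4 plans individual listings, not a summary.

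There are thus two separate gaps: whether the underlying condition is reported can depend on the site, and the minor amputation itself is not counted under either reading.

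**The case against.** The strongest reply rests on Section 8.4. If amputation is a treatment and never the AE term, a list item that excludes a procedure agrees with that rule. It excludes the care and leaves the condition reportable. Serious events also remain: Section 8.5 requires all SAEs through 6 months and index-limb SAEs through 3 years. The list is guidance, the data are collected at visits, and deterioration of the foot would also show in the Rutherford and wound-healing endpoints.

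Much of this stands. A reader might infer that the protocol declares minor amputations never to be adverse events, whatever their timing or cause. The text does not say so. That reading comes from the item's silence and ignores both the investigator's discretion and the presenting-condition rule. Nor do the documents show that tissue loss itself is excluded, or that the Data Monitoring Committee would not see it: the committee's charter is not among them.

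What the reply does not settle is consistency. The item names minor amputations without pointing to Section 8.4 or to the pre-planned definition, and discretion at up to 25 sites allows different answers to the same event. Collection on a visit form is also not a planned analysis.

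**Conclusion.** The point holds as a conflict in the reporting rules together with a missing summary. The Section 8 item should be reconciled with Sections 8.4 and 15, and the SAP should count minor amputations of the index limb.

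Its size cannot be estimated. The documents give neither a rate of minor amputation nor the share that is pre-planned, so any number of affected subjects would be invented. A reader might also infer that the safety profile will look better than it was. The documents support only that it could, if sites take the narrower view of what is reportable.

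The conclusion assumes that at least some sites would read the item literally and that no unseen charter or form instruction already narrows it. The primary endpoint is unaffected, because it counts only above-ankle amputation and death.

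**What to change.** 1. **Protocol Section 8.** Limit the item to debridement and to pre-planned minor amputations as defined in Section 15. State that for any other minor amputation of the index limb, the presenting condition is reported as the AE with amputation as treatment, and as an SAE when it meets the Section 8.4 criteria. Say in the same place how an overnight observation stay is classed.

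2. **SAP Section 8.** Add a descriptive table of index-limb minor amputations by time point for all mITT subjects, taken from the Table 1 assessments and split into pre-planned (documented before the index procedure) and not pre-planned.

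The second change matters more now. SAP Section 4 places the reduction of the maximum sample size after the N=90 assessment, so most subjects were enrolled before any new wording could apply, and a change to the AE rule alone would leave two reporting regimes in one table. A table built from the visit assessments gives one consistent count across both periods.

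The cost is one protocol amendment and one table. The reported AE/SAE rate will probably rise. Source records will have to be checked for pre-planned status if the eCRF does not hold it, since Section 15 places that documentation in the medical record. The change concerns reporting only and alters no treatment decision.
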